After the account is created, participants will complete two electronic baseline surveys on an in room device during this initial clinic visit: the 36-Item Short Form Survey (SF-36) and the Self-Efficacy for Home Exercise Programs Scale (SEHEPS). The link for these REDCap surveys will be imbedded in Thinkific. A study team member will be available to assist in creation of the Thinkific account or completion of these initial surveys. Participants will leave their initial clinic appointment with a packet containing: a 3 pack of resistance bands, a copy of their consent form and a copy of the informational packet about the exercise program (see attached) that can otherwise be accessed through the Thinkific course.

Participants will additionally access the Thinkific account at home to complete an exercise based prehabilitation course. This course will provide video and written instruction on how to perform each exercise safely, as well as how to properly increase the intensity of the program, (e.g. resistance, number of repetitions and sets). This program will also include links to the American College of Surgeons alcohol related recommendations and the Maine QuitLink for tobacco/smoking and vaping cessation that patients may access if applicable. Participants will be instructed to perform daily exercise and keep track of their exercise in either a handwritten or electronic log (see attached document) until their surgery or until the final clinic visit if surgery is ultimately not performed. The log is available as a paper copy provided at the first visit and as a pdf embedded in the Thinkific course.

<https://mainehealth.thinkific.com/courses/prehab-exercise>

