Repeat self-administered survey with the SF-36 will become available through a direct email link from REDCap at two and four weeks after initiation of the prehabilitation program. If participants do not complete the surveys, they will receive a reminder email, generated automatically by REDCap, at 24 and 48hrs after the initial email was sent (please see attached screen shot of emails). At the final clinic visit prior to surgery, the participant's exercise log will be collected by the study team. The participant's exercise log will either be physically brought to clinic or uploaded by the participant through the Thinkific platform prior to this final appointment. Repeat frailty screening, with the RAI, will be performed by the surgical oncology clinic nursing staff at every follow up clinic appointment until surgery as part of the patients' normal care.

Participants will complete a final self-administered SF-36 survey and a survey to assess their satisfaction with the exercise prehabilitation program anytime during the week leading up to their surgery, or the week after their final appointment if they ultimately are not a surgical candidate. The link to this final REDCap survey is embedded in Thinkific. The surgeon will remind patients at their final clinic visit to complete these surveys.

During the extent of the study, if patients have questions pertaining to the study they will be able to contact their surgeon at any time by contacting the surgical oncology clinic. If the patient has questions or concerns related to the performance of the prehabilitation program exercises, they will be directed to a licensed physical therapist.

Please reference to the attached material to view each of the following surveys:

Risk Analysis Index (RAI):

The RAI is a validated frailty screening tool that was developed and implemented at the University of Nebraska. Components of the RAI include nursing home admission, unintentional weight loss, renal failure, congestive heart failure, poor appetite, gender, shortness of breath, malignancy, age, cognition, and activities of daily living.²⁰

36-Item Short Form Survey (SF-36):

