We believe that most individuals will benefit by participating in this study. Participants are likely to see improvements in strength and endurance to participation in a regular exercise program. Further, these improvements may help participants recovery from surgery. This pilot study would be the first step towards offering surgical patients what is becoming standard of care. The data collected will be used to benefit patients in the future. If the results of this pilot study support our hypothesis, it is likely the prehabilitation program will be implemented widely for surgical patients at MMC. This holds the potential for a large positive impact in the future by reducing negative post-surgical outcomes. This likely has the benefit of not only improved quality of life and functionality for the patient, but also decreased healthcare utilization and cost.

POTENTIAL PROBLEMS

- Loss to follow up: As a prospective study, patients enrolled may be loss to follow up. Some reasons include if a patient transitions care to a different provider or moves. The study team will make efforts to maintain all participant and will perform phone calls if needed to re-engage participants that may have been lost. (please see phone script)
- Technology: One of the inclusion criteria for this study is home internet access and established email account. Having these does not mean a participant will be proficient in using the internet. They may struggle to access or use the technology. To try and combat this, we have made care members easily available to answer questions and help participants trouble shoot.

TIMELINE

Because this intervention is recommended in most perioperative protocols, we hope to implement this program as soon as possible. Our goal is to recruit 20 patients within three months. Each patient will participate in the prehabilitation program for at least two weeks. It is

difficult to predict how long a patient will be in the program because the duration depends on when their surgery is eventually scheduled. This is individualized, and typically ranges from two weeks to six months. We hope to complete data collection in seven months. At that time, we hope to complete data analysis and submit an abstract by July, 2022.

REFERENCES

1. 2019 profile of older americans. In: Living USDoHaHSAoC, ed2019:5-6, 17-18.

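### Adherence rests on a log due only once, at or before the final visit, so a participant lost earlier will usually leave no adherence data

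*Combined protocol and SAP*

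**What the plan says.** Specific Aims makes adherence the first feasibility measure (1a), to be read from logs that participants keep. Aim 1b relates the pre-program self-efficacy score to adherence. No other adherence source is named.

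Study Procedures describes the log and its return:
- Form: "The log is available as a paper copy provided at the first visit and as a pdf embedded in the Thinkific course".
- Return: at the final clinic visit before surgery the participant's "exercise log will be collected by the study team". It is either brought in on paper or "uploaded by the participant through the Thinkific platform prior to this final appointment". No earlier submission date is set.

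The same section sets the other contacts. The repeat SF-36 "will become available through a direct email link from REDCap at two and four weeks after initiation of the prehabilitation program", with reminders "generated automatically by REDCap, at 24 and 48hrs after the initial email was sent". Nursing staff repeat the RAI at follow-up appointments as routine care. A final SF-36 and a satisfaction survey fall in the week before surgery, or in the week after the final appointment if there is no surgery.

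On time in the program, Timeline says: "This is individualized, and typically ranges from two weeks to six months". Study Population sets enrolment at 20 and accepts that some will be lost. Potential Problems says the team "will perform phone calls if needed to re-engage participants that may have been lost". Data Analysis gives no rule for a participant without a log.

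**The concern.** A single collection at the end makes adherence all or nothing for each participant. Someone who moves or transfers care, the two losses that Potential Problems itself names, takes the whole record along, including weeks already completed. The same holds for a paper log that is mislaid.

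Two things are at stake. First, Aim 1a would be estimated only on those retained, who are plausibly the better adherers, so the program could look more feasible than it is. Second, Aim 1b loses the same participants from its regression, and loses them according to the outcome being modelled. This matters because the protocol says that favourable results would probably lead to wide use of the program at the center.

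**Working it through.** There is no planned figure to reproduce. The 20 is a pilot size, and Data Analysis says that the parameters for a power calculation were not available. The check covers timing, and what lost logs do to the estimate.

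**1. Which contacts yield adherence data**
- Baseline visit: SF-36 and SEHEPS; a blank log is provided.
- Weeks 2 and 4: SF-36 by email, reminders at 24 h and 48 h. This is a health-status measure; no log is requested.
- Follow-up clinic appointments: RAI. No log check is described.
- Final clinic visit: the log is collected, unless already uploaded.
- Around surgery or the final appointment: SF-36 and satisfaction survey.

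Only the final visit, or an upload the participant chooses to make before it, yields the log.

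**2. Length of program after the last study email**

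For a program of W weeks, the share after week 4 is (W − 4)/W, or zero if W ≤ 4.
- W = 2 or 4: 0
- W = 8: 4/8 = 50%
- W = 12: 8/12 = 67%
- W = 26: 22/26 = 85%

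Routine clinic visits may fall inside this span.

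**3. Uncertainty from missing logs**

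Inputs: N = 20 (Study Population); L participants without a log, assumed to be 0 to 6 because the documents give no rate (10% × 20 = 2; 30% × 20 = 6). The text supplied sets no threshold for calling a participant adherent, so 50% adherent among returned logs is purely illustrative. With x adherent among 20 − L returned logs, the share over all 20 lies between x/20 (all lost non-adherent) and (x + L)/20 (all lost adherent). The width is L/20 whatever x is. Intervals are exact 95% (Clopper-Pearson).
- L = 0: 10/20 = 50%, interval 27% to 73%; no further range.
- L = 2: 9/18 = 50%, interval 26% to 74%; range 9/20 to 11/20 = 45% to 55%.
- L = 4: 8/16 = 50%, interval 25% to 75%; range 8/20 to 12/20 = 40% to 60%.
- L = 6: 7/14 = 50%, interval 23% to 77%; range 7/20 to 13/20 = 35% to 65%.

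If every lost participant were non-adherent, the figure from returned logs would be too high by 50 − 45 = 5 points at L = 2 and by 50 − 35 = 15 points at L = 6.

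**4. What early uploads would recover, and how they must be scored**

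A week-4 upload keeps up to 28 days per participant. Suppose someone logs all 28 days, uploads, and is then lost from a 26-week (182-day) program. With unobserved days excluded, adherence is 28/28 = 100%; with them counted as non-adherent, it is 28/182 = 15%. Treating the upload as the record for the whole program would report only the 100%, and so would bring back the upward bias. Both figures are needed.

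**The case against.** A reader might infer that contact stops at week 4, that nobody can tell when a participant has stopped exercising, and that a lost participant necessarily leaves nothing. The documents do not support this:
- RAI appointments, the final visit and the final surveys can all come after week 4. Unanswered week-2 and week-4 surveys can also reveal disengagement.
- Someone who stops in week 6 but attends the final visit hands in a log that shows it. Aim 1a asks for adherence to be evaluated, not detected as it happens.
- The Thinkific upload has no earliest date, so an early voluntary upload would survive, and a re-engagement call might recover a log.
- The 85% applies only at six months. If recruitment (three months) and data collection (seven months) both run from study start, six months fits only those enrolled in about the first month (7 − 6 = 1); the last enrolled have about 7 − 3 = 4 months.
- The final visit belongs to planned cancer care, which should limit loss. The study is exploratory and expects attrition.
- The phone script, log form and data collection document are attachments not supplied here, and could add detail.

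All of this stands, and it narrows the point to participants who do not reach the final visit with a log. It does not remove that point. The later contacts need a participant who still attends, none before the final visit is described as collecting or checking the log, and an upload that nobody requests cannot be relied on. The exploratory label affects how p-values are read; it does not correct a feasibility estimate based on those who stayed.

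**Conclusion.** The point holds in limited form. With the plan followed exactly, a participant lost before the final visit will usually contribute nothing to Aims 1a and 1b, and the adherence estimate describes those retained. With 2 to 6 of 20 lost, the resulting uncertainty over all enrolled is 10 to 30 percentage points, on top of exact intervals already about 48 to 54 points wide in the illustration (74 − 26; 77 − 23).

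This rests on two assumptions: a loss of 10% to 30%, which has no source in the documents, and a link between loss and poor adherence, which is plausible but not documented. With no losses and every log returned, the problem disappears. It calls for a modest change to data collection and a stated analysis rule; it does not show that the study cannot assess adherence.

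**What to change.** 1. Add a field to the existing week-2 and week-4 REDCap surveys asking the participant to upload or photograph the log so far, under the same 24 h and 48 h reminders. Add this route to Data Management, which now describes log review through Thinkific or Epic only.
2. In Data Analysis, define adherence for all enrolled participants as days logged over days in the program, and state which end date applies to someone who is lost.
3. For anyone without a final log, use the uploaded weeks as observed and do not carry them forward as the whole-program record. Report the result with unobserved days counted as non-adherent and with them excluded, and give the number without a final log.

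Cost: a form field, and staff time to check receipt and enter the data. The request may itself prompt some exercise, but the effect should be small because an email already goes out at those times. Some missing uploads will reflect technical difficulty, which Potential Problems already foresees, so a missing upload should not by itself be read as non-adherence. The gain is partial: in a 26-week program, weeks 5 to 26 would still be unobserved for someone lost after week 4.

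Four-weekly requests after week 4, and calls triggered by a missing upload, would close more of that gap. They are optional: they add monitoring to a program that Anticipated Risks and Benefits describes as designed for independent use, and could change the adherence being measured.

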Implementation of a prehabilitation program will be feasible and will improve clinical status.

SPECIFIC AIMS

We propose to pilot (N=20) and assess a new prehabilitation program for frail surgical oncology patients. We will:

1. Assess feasibility. We will:
 - a. Evaluate adherence through analysis of patient maintained exercise logs.
 - b. Assess self-efficacy by evaluating the relationship between pre-program self-efficacy score and adherence.
 - c. Assess patient satisfaction and barriers to adherence through a post prehab program survey.

2. Assess clinical impact. We will:
 - a. Evaluate health-related quality of life before and after participation in the prehabilitation program.
 - b. Evaluate frailty before and after participation in the prehabilitation program.

METHODS

Study Design: Prospective cohort study

This longitudinal study will be a prospective, non-randomized, within-subject design focused on patients diagnosed with complex gastrointestinal (GI) cancer evaluated and treated at Maine Medical Center by the Surgical Oncology Service. All subjects who meet the inclusion criteria will be offered the opportunity to be enrolled; these recruitment efforts will cease when planned enrollment is complete. Participants will complete a prehabilitation exercise program through the Thinkific platform. Data on frailty, quality of life, self-efficacy and adherence will be collected through surveys and patient maintained exercise logs.

Study Population

Participants will be selected from the population of patients at the MMC Surgical Oncology Clinic. Patients at this clinic are being evaluated for surgical treatment of oncologic diseases such as colorectal or pancreatic cancer. Under normal circumstances, patients are seen for an initial consultation where a treatment plan is created. Patients either have surgery or chemotherapy up front. If the patient has surgery as the first treatment, the surgery is scheduled at that initial appointment. If the patient has chemotherapy before surgery, they will return for at least one more appointment after completion of chemotherapy. Their surgery is scheduled at this follow-up appointment. This process can span anywhere from 4 weeks to 6 months.

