SF-36 is a well-researched, self-reported measure of health which stems from the Medical Outcomes Study. It comprises 36 questions which cover eight domains of health: Limitations in physical, social or usual role activities due to physical or mental health problems, bodily pain, general mental health (psychological distress and well-being), vitality (energy and fatigue), and general health perceptions. This measure is now widely utilized by managed care organizations and by Medicare for routine monitoring and assessment of care outcomes in adult patients.²¹

Self-Efficacy for Home Exercise Programs Scale (SEHEPS):

The SEHEPS is a clinically useful tool to evaluate patients' self-efficacy in home-based musculoskeletal exercise programs. It is a 12-item patient-reported questionnaire on which patients rate their confidence in performing home-based exercise on a 7-point scale.²²

Satisfaction Survey:

This survey was developed in house by the study team because an appropriate validated tool could not be found in the literature. It will utilize a Likert-type rating scale to assess participant satisfaction with the Thinkific platform and the video/handout instructions. Additionally, it will evaluate the participants' perceived mental and physical benefit from the program. See attached survey.

DATA COLLECTION, MANAGEMENT, AND ANALYSIS

Data Collection

Data pertaining to the patient demographics and baseline characteristics will be collected by the study team through manual extraction from Epic. Data from the participants exercise logs will be manually extracted by the study team from either the Thinkific platform or Epic depending on how the participant submitted this form (i.e. electronically on Thinkific or manually bringing the log to their appointment for uploading to Epic by the study staff). The surveys will be completed electronically in the office setting on the exam room computer or online at home through REDCap (via emailed link or a link to REDCap embedded in Thinkific). These data will automatically upload to REDCap. Please refer to the master list and data collection document submitted with this proposal for a list of variables that will be collected.

Data Management

All data will be collected and maintained in a REDCap database to which only the study team will have password protected login access. The data collected through manual extraction from EPIC will be entered into REDCap by members of the study team. Data from the RAI surveys

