performed as part of routine care will be initially recorded in Epic then manually transferred into REDCap.

Data from the SF-36, SEHEPS and satisfaction survey will be directly submitted into REDCap from either an emailed link or link embedded in Thinkific. Once uploaded, the participants formula ID (first two letters of first name + first two letters of last name) and email, will help us manually link the survey entry to the master list and the second survey data collection form. Of note, the participant will only enter their email and formula ID at the beginning of the first and last surveys. The email entry is necessary to send out the 2 week and 4 week surveys. The email will also serve as a second patient identifier if participants have identical formula IDs. When more than one survey is completed on the same day, the separate surveys are linked together through REDCap. This means the participants only need to type their formula ID and email once, despite completing multiple surveys. (please see the attached email chain and document from [name] regarding REDCap security and her support for this plan)

The exercise logs will be reviewed by the study team in Thinkific or through Epic, if the participant brought a paper log, then entered into REDCap. If participants bring a paper form of their exercise log, it will be scanned into their EPIC account by a member of the study team and the paper copy of the exercise log will be shredded after the image has been uploaded into Epic. The signed consent form will be secured in a locked file cabinet behind a locked office door in the Surgical Oncology Department at [name].

A master list will be maintained in REDCap separate from other study documents. Only a study ID, consisting of the first 2 letters of the first and last name, will link this master list to the two data collection files on REDCap. Once the data collection is finalized, the master list will be deleted. The limited data set that remains will then be exported as a CSV file that will be maintained as an encrypted file on a password protected MMC institution desktop. This limited dataset will be accessed only from MMC computers and only by MMC study team listed above and by members of the IRB if needed.

All regulatory documents and files associated with the study (IRB documents, HIPAA-related documentation) will be maintained for a minimum of 6 years after the final publication/report and then deleted/destroyed.

Data Analysis

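### The end-of-program survey serving Aim 1c gets weaker follow-up than the interim SF-36 among participants who disengage, so barriers to adherence are likely to be under-reported

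*Combined protocol and SAP*

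**What the plan says.** Specific Aims, item 1c: "Assess patient satisfaction and barriers to adherence through a post prehab program survey".

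The Satisfaction Survey section describes an in-house Likert-type form that will "assess participant satisfaction with the Thinkific platform and the video/handout instructions". It then adds that "it will evaluate the participants' perceived mental and physical benefit from the program. See attached survey".

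Study Procedures has the final SF-36 and this survey completed "anytime during the week leading up to their surgery, or the week after their final appointment if they ultimately are not a surgical candidate". On access it says: "The link to this final REDCap survey is embedded in Thinkific". The prompt it describes is a reminder from the surgeon at the final clinic visit. The same section sends the two- and four-week SF-36 by direct REDCap email, with automatic reminders at 24 and 48 hours to those who have not answered.

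Data Management is more general: "Data from the SF-36, SEHEPS and satisfaction survey will be directly submitted into REDCap from either an emailed link or link embedded in Thinkific". It also explains why an address is collected: "The email entry is necessary to send out the 2 week and 4 week surveys".

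**The concern.** Barriers to adherence are best known to the people who met them, and some of those people will have stopped. Yet the survey that has to capture barriers appears to sit inside the platform they may have left. It is prompted once, by the surgeon, at a visit they may not attend. The interim SF-36, which carries no feasibility question, has the stronger delivery.

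Feasibility is the first aim, and the protocol foresees wide use of the program if the pilot supports its hypothesis. If replies come disproportionately from participants who stayed engaged, the program will look better liked and less obstructed than it was. The team would then know less about what to change before wider use.

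**Working it through.** The documents give no response rate, dropout rate or expected adherence, and the enrollment target of 20 has no derivation. There is no planned figure to reproduce. The check sets the sections side by side and then works out the direction of any bias.

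1. **Content.** Aim 1c asks for two things: satisfaction and barriers. The Satisfaction Survey section describes ratings of the platform and instructions, and "perceived mental and physical benefit from the program". Such ratings could reveal difficulty with the technology or unclear instructions. They would not obviously reveal symptoms, treatment effects, lack of time or loss of motivation. No other section describes collecting reasons for missed sessions or for stopping.

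2. **Route.** The sentence specific to the final survey puts its link in Thinkific. Data Collection and Data Management mention an emailed link or a Thinkific link for the surveys as a group, without saying which survey uses which. Two details favor the Thinkific reading. Data Management names only the two- and four-week mailings as the reason for needing the address. It also has participants type their identifiers only at the first and last surveys, which are the two that Study Procedures places in Thinkific.

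3. **Prompts.** Interim SF-36: a direct email and two automatic reminders. Final surveys: the surgeon's reminder, which reaches only those who attend the final visit and may come before the one-week pre-surgery window opens. No automatic reminder is described.

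4. **Timing.** The two windows are tied to surgery, or to the final appointment of someone who proves not to be a surgical candidate. No window is stated for a participant who leaves the service, although Study Population expects some attrition.

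5. **Direction.** Let w be the share of enrolled participants who disengage. Let r_d and r_e be the response rates of disengaged and engaged participants, and p_d and p_e the proportions in each group who would report a given barrier.
   - True proportion: T = w·p_d + (1 − w)·p_e
   - Disengaged share of replies: v = w·r_d / [w·r_d + (1 − w)·r_e]
   - Expected observed proportion: O = v·p_d + (1 − v)·p_e
   - Difference: O − T = (v − w)(p_d − p_e)

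   If r_d < r_e, then v < w. A barrier more common among the disengaged (p_d > p_e) is then understated. The same formula applied to satisfaction, with p_d < p_e, gives an overstatement. If the response rates are equal, the difference is zero. None of w, r_d, r_e, p_d or p_e is in the documents, so the sign can be argued but the size cannot. Each person is 1/20 = 5% of the planned sample, so a few missing replies matter.

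**The case against.** Several points on the other side have weight.

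- **The form is an attachment.** A reader might infer that the survey has no barrier question. The documents do not support that: the protocol gives a short summary and points to a form not in the reviewed text. What stands is that the summary does not name an item for half of Aim 1c.
- **The route is not settled.** A reader might infer that the survey can be reached only by logging back into the course. The specific sentence favors that reading, but the general wording allows an emailed link. What stands is the ambiguity, and the absence of any described automatic reminder.
- **Safeguards exist.** The surgeon's reminder reaches anyone who attends, whether or not they exercised. Patients who do not go to surgery have a window of their own. Potential Problems plans phone calls to re-engage people who may be lost. A reader might infer that the barriers of those who stopped will be missed altogether; that would require none of them to reply, which nothing in the documents implies. However, the calls are not said to ask about barriers, and the reminder does not reach those who miss the visit.
- **Leaving the platform is not the same as stopping exercise.** Participants also receive a paper information packet and can keep a paper log, so some may adhere without Thinkific, and some who stop may still open the link. This weakens the link between platform use and adherence but does not remove it. Potential Problems itself warns that some participants may find the technology hard to use, and a survey placed behind that technology will tend to lose them.
- **Other feasibility data are collected.** Logs, baseline self-efficacy and a count of phone calls will all inform program design, so it would be too strong to say the pilot cannot show what to change.

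**Conclusion.** The point holds as a delivery weakness with a content question attached. Followed as written, the plan gives the survey for Aim 1c its weakest follow-up among participants who disengage. Barriers are likely to be under-reported and satisfaction over-reported.

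This rests on two assumptions: that participants who leave the course or miss the final visit reply less often than the rest, and that they differ in barriers and satisfaction. Both are plausible, but neither is documented. The size is unknown, and any percentage would come from invented rates. The content question is open until the attached form is checked. This is an inexpensive improvement that should be made; it does not invalidate the pilot.

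**What to change.** 1. Send the final SF-36 and satisfaction survey by direct REDCap email to every enrolled participant, with the same 24- and 48-hour reminders used for the interim surveys. Include those who stopped the exercises or withdrew from the program but not from follow-up. Trigger the email once the surgery date or final visit is known.
2. Keep the Thinkific link as a second route, and make Study Procedures, Data Collection and Data Management agree on how the final survey is delivered.
3. Report how many enrolled participants responded, alongside logged adherence. Do not split results into adherent and non-adherent groups, because the protocol defines no cut-off.
4. Confirm that the attached survey contains a barrier item and name it in the Satisfaction Survey section. If it does not, add a single item on reasons for missed sessions.

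Cost: the addresses are already collected at the first survey and the reminder process is already in use. The final email is not a fixed interval from the start of the program, so someone must set each send date by hand. A minor IRB amendment is needed. Visits, sample size and the exercise program do not change.
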